Appendix 3. STATISTICAL METHODOLOGY DETAILS

Appendix 3.1. Further Details of Interim Analyses

Details of the ongoing review of safety data (including joint safety events) are given in a separate statistical analysis plan for the Data Monitoring Committee.

Appendix 3.2. Further Details of the Statistical Methods

A description of the combination of the ANCOVA results from each of the multiple imputed datasets is given below, and taken from Little & Rubin (2002),³ page 86-7.

In this analysis we have defined the number of imputations (D) to be 100.

The treatment estimates for individual treatment groups and treatment contrasts are defined as θ_i for $i = 1 \dots D$. The combined estimate is $\bar{\theta}_D = \frac{1}{D} \sum_{i=1}^D \theta_i$. The variability of the combined estimate contains components of both Within- (W) and Between- (B) imputation dataset variability. These are shown below:

$$\bar{W}_D = \frac{1}{D} \sum_{i=1}^D W_i \text{ and } B_D = \frac{1}{D-1} \sum_{i=1}^D (\hat{\theta}_i - \bar{\theta}_D)^2$$

where W_i is the variance for the parameter θ_i .

The total variance for $\bar{\theta}_D$ is shown below:

$$T_D = \bar{W}_D + \frac{D+1}{D} B_D.$$

The test statistic $\frac{(\theta - \bar{\theta}_D)}{\sqrt{T_D}}$ has a t-distribution with v^* degrees of freedom, which is defined below:

$$v^* = \left(\frac{1}{v} + \frac{1}{\hat{v}_{obs}} \right),$$

using

09001776493181b656\Approved\Approved On: 03-Oct-2019 08:56 (GMT)

$$v = (D - 1) \left(1 + \frac{1}{D + 1} \frac{\bar{W}_D}{B_D} \right)^2$$
$$\hat{v}_{obs} = (1 - \hat{\gamma}_D) \left(\frac{v_{com} + 1}{v_{com+3}} \right) v_{com}$$
$$\hat{\gamma}_D = \left(1 + \frac{1}{D} \right) \frac{B_D}{T_D}.$$

This distribution can be used to construct the test statistics and 95% confidence intervals for θ .

09001776e4931781b656\Approved\Approved On: 03-Oct-2019 08:56 (GMT)

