### 9.1. Sample Size Determination

A sample size of approximately 1000 subjects for each of the treatment groups of NSAID, tanezumab 2.5 mg and tanezumab 5 mg will be used in this study. This sample size allows for a high probability of observing subjects with any component of the composite endpoint where the event rate over this study is very small. If the event rate were 0.25%, then there would be a >90% probability of observing at least one subject with an event in any single treatment group.

In addition, the sample size allows for good precision to estimate the incidence rate for each treatment group in order to estimate an upper bound for the true incidence rate. The table below gives the width of the 95% confidence intervals for the individual treatment groups with this sample size.

Observed Rate of Rapidly Progressive Osteoarthritis Type 2	95% Confidence Interval for Individual Treatment Groups (N=1000)
0%	[0, 0.37%]
0.1%	[0.00, 0.56%]
0.2%	[0.02, 0.72%]
0.3%	[0.06, 0.87%]
0.4%	[0.11, 1.02%]
0.5%	[0.16, 1.16%]
1.0%	[0.48, 1.83%]

Table IV. Estimated Event Incidence Kate Precision	Table 10.	Estimated Event Incidence Rate Precision
--	-----------	---

For the assessment of the incidence of subjects with a total joint replacement, a sample size of approximately 1000 subjects per group would be sufficient to demonstrate a significant difference ( $p \le 0.05$ ) between any two treatment groups, for a difference of 2% with an observed control group rate for total joint replacement of 2%. Similarly, for the assessment of the incidence of subjects with an adjudication outcome of rapidly progressive osteoarthritis type 2, a sample size of approximately 1000 subjects per group would be sufficient to demonstrate a significant difference ( $p \le 0.10$ ) between any two treatment groups, for a difference of 1% with an observed control group rate for rapidly progressive osteoarthritis of 0%.

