For the efficacy assessments, a sample size of approximately 1000 subjects per group gives 76% power for the treatment comparisons of both tanezumab 5 mg versus NSAID and tanezumab 2.5 mg versus NSAID all three co-primary efficacy endpoints, for assumed treatment differences of -0.73/-0.45 (tanezumab 5 mg/2.5 mg versus NSAID), -0.80/-0.53 and -0.21/-0.11 for WOMAC Pain subscale, WOMAC Physical Function subscale and the Patient's Global Assessment of Osteoarthritis, respectively. The within-group standard deviations were 2.73, 2.58 and 0.92 for WOMAC Pain subscale, WOMAC Physical Function subscale function subscale and Patient's Global Assessment of Osteoarthritis, respectively. The correlation of

the change from Baseline to Week 16 value for WOMAC Pain subscale versus WOMAC Physical Function subscale was 0.93. The correlations between Patient's Global Assessment of Osteoarthritis and WOMAC Pain and Physical Function subscales were approximately 0.68.

For the Japanese specific efficacy assessments, a sample size of 1000 subjects per group gives 95% power for the treatment comparisons of both tanezumab 5 mg versus NSAID and tanezumab 2.5 mg versus NSAID two co-primary efficacy endpoints, for assumed treatment differences of -0.73/-0.45 (tanezumab 5 mg/2.5 mg versus NSAID) and -0.80/-0.53 for WOMAC Pain subscale and WOMAC Physical Function subscale, respectively. The within-group standard deviations were 2.73 and 2.58 for WOMAC Pain subscale and WOMAC Physical Function subscale of Osteoarthritis, respectively. The correlation of the change from Baseline to Week 16 value for WOMAC Pain subscale versus WOMAC Physical Function subscale was 0.93.

A sample size of approximately 220 subjects per treatment group is required within each of the three NSAID cohorts (celecoxib, naproxen and diclofenac). This sample size would give an 80% power to detect statistical significance at the 5% significance level, for the comparison of tanezumab 5 mg versus individual NSAID groups in the WOMAC Pain subscale, assuming a treatment difference of -0.73 and a within-group standard deviation of 2.73.

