#### 9.2. Primary Analysis

### 9.2.1. Analysis of Primary Endpoints

The incidence of subjects with any of the adjudication outcomes of rapidly progressive osteoarthritis (type-1 or type-2), subchondral insufficiency fracture (or SPONK), primary osteonecrosis, or pathological fracture (primary composite endpoint) will be shown by number of subjects treated and subject years of exposure (treatment plus follow-up periods), for individual treatment groups and differences between tanezumab treatment groups and the NSAID treatment group. The risk ratio and risk difference with 95% confidence intervals will be calculated for the comparisons of each tanezumab treatment group versus the NSAID treatment group, as well as significance tests for each treatment comparison. The time to each event will be summarized, and (where there are sufficient numbers of subjects) Kaplan-Meier estimates of the time to event will be produced, together with an analysis of each tanezumab treatment group using the log-rank test.

The primary safety and efficacy population will be the ITT population, defined as all randomized subjects who received SC investigational product (either tanezumab or matching placebo). The primary efficacy analysis will use multiple imputation methods for missing data at Week 16. Details of the multiple imputation procedure are given below. All treatment comparisons will use the two-sided 5% significance level.

The co-primary efficacy endpoints will be analyzed using an ANCOVA model, with model terms for Baseline score, Baseline Diary Average Pain, index joint (hip or knee), Kellgren-Lawrence grade, NSAID cohort (diclofenac, celecoxib or naproxen) and treatment group, and study site as a random effect. The assessment of significance for the tanezumab SC versus NSAID treatment contrasts of the primary efficacy parameters will use a step-down testing strategy within each of the co-primary efficacy endpoints. This order of significance testing is defined as first testing tanezumab 5 mg versus NSAID, and if statistically significant ( $p \le 0.05$ ) to then test tanezumab 2.5 mg versus NSAID. Finally, the tanezumab dose group is declared as superior to NSAID if the corresponding treatment contrast is significant over all three co-primary endpoints (*two co-primary efficacy endpoints in Japan*). This testing procedure will maintain the Type I error to 5% or less within each of the co-primary efficacy endpoints (*two co-primary efficacy endpoints in Japan*).

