One hundred imputed samples will be used in this analysis. In order to pre-define the analysis (and not to allow the results to change if run again), the following seeds will be used in the creation of the multiple imputed data: WOMAC scores [1] 7001-7100; and [2] 8001-8100; PGA scores: [3] 9001-9100 and [4] 10001-10100; and diary pain scores: [5] 11001-11100 and [6] 12001-12100. Imputed data for the PGA will be rounded to integer scores in the range 1 to 5. Imputed data for the WOMAC subscale and Average scores, and for the diary pain scores <0 and >10 will be truncated to 0 and 10, respectively. Imputed data for the WOMAC items of Pain when Going Up or Down Stairs and Pain when Walking on a Flat Surface will be rounded to integer scores in the range 0 to 10. The ANCOVA analysis described in [Section 8.1.1](#) (with covariates in [Section 6.4](#)) will be used for each imputation dataset, and the overall results will be calculated to take account of the variability both within and between imputation datasets using standard methods (Little & Rubin, 2002), which are described in [Appendix 3.2](#).

0900177ed1931781b0561ApprovedApproved On: 08-10-2019 08:56 (GMT)

This analysis will be used for the co-primary efficacy endpoints at Week 16, plus secondary analyses at other time points, and also for a range of secondary efficacy endpoints at all time points up to Week 56. When using the multiple imputation method described above for time points earlier than Week 56, then the reason for missing data is assessed up to the end of the window for that particular time point (see [Appendix 1.1](#)).

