8.1. Statistical Methods

8.1.1. Analyses for Continuous Data

The mixed model ANCOVA, with multiple imputation, will be used with continuous change from Baseline endpoints for landmark (single time point) analyses. The model will include the covariates described in [Section 6.4](#), including study site as a random effect. Estimates of treatment effects and pair wise treatment comparisons will be done using least squares means (LS means) and 95% CIs.

Under the primary analysis using multiple imputation defined in [Section 7](#), the multiple ANCOVA results will be combined using standard methods (Little & Rubin, 2002)³, which are described in [Appendix 3.2](#).

A sensitivity analysis for the primary endpoints will use a mixed model repeated measures analysis, with covariate terms for Time (study week, treated as a categorical variable), Treatment Group and Time-by-Treatment interaction, as well as the covariates described in [Section 6.4](#). The unstructured covariance will be used in the modeling of the within-subject errors in the analysis. Even though this is a sensitivity analysis for the primary endpoints, estimates for the time points of Weeks 2, 4, and 8, in addition to Week 16 will be shown from this analysis.

Interaction analyses will be performed for the primary endpoints, exploring the effect of Study site and Country. These analyses will fit the covariate terms described in [Section 6.4](#) (except for use of Study site as a covariate in the Country interaction analysis, where Country will be used instead [as a fixed term]), in addition to the interaction term of treatment group by factor.

The interaction of Treatment with Study site will be fitted as a random effect (in addition to Study site itself), with the resulting estimated treatment differences being shown for the largest study sites to illustrate the level of consistency of treatment benefit across the larger study sites. The study sites to be examined in this way will be any site with an average of ten or more subjects per treatment group within the site, which for this study relates to any site with 30 or more subjects in total. This assessment will be made prior to unblinding, therefore a study site in this group may still have fewer than ten subjects in one or more of the treatment groups, however that site will still be included in this summary of efficacy of the

0900177ed193181b050ApprovedApproved On: 03-Oct-2019 08:56 (GMT)

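### SAP Appendix 3.2 puts 1/(D+1) where its own variance formula requires D/(D+1) in the degrees of freedom for combining imputations, so the co-primary confidence intervals are slightly too wide

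*SAP*

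**What the plan says.** The primary analysis of the co-primary endpoints fits the ANCOVA to each imputed dataset and pools the results. SAP Section 7 states "One hundred imputed samples will be used in this analysis", and Section 8.1.1 says "the multiple ANCOVA results will be combined using standard methods". Both sections refer to Appendix 3.2 for the description.

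Appendix 3.2 states "In this analysis we have defined the number of imputations (D) to be 100" and then defines, with W the average within-imputation variance and B the between-imputation variance:

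- total variance: T = W + ((D+1)/D)B
- fraction of missing information: γ = (1 + 1/D)B/T
- degrees of freedom: "v = (D - 1) \left(1 + \frac{1}{D + 1} \frac{\bar{W}_D}{B_D} \right)^2"
- observed-data degrees of freedom v_obs, built from γ and the complete-data degrees of freedom v_com
- final degrees of freedom v*, built from v and v_obs

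The appendix says that the resulting t-distribution supplies the test statistics and 95% confidence intervals. No other section gives a different formula.

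**The concern.** The coefficient on W/B in v does not fit the T and γ around it. With D = 100 it is 100 times too small. As D grows, 1/(D+1) tends to zero, so the printed v falls back to about D − 1 however little information is missing. The formula then loses nearly all the dependence on missing information that it is meant to carry.

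The quantity v sets the reference distribution for the primary p-values and intervals. SAP Section 4.2 requires all three co-primary endpoints to be significant for a dose before testing moves on. A prespecified critical value should therefore not depend on a slip in a formula.

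**Working it through.** **Inputs from the documents.** D = 100, and T, γ and v as printed (SAP Appendix 3.2). The test level is two-sided 5% (Protocol 9.2.1: "All treatment comparisons will use the two-sided 5% significance level"). There are about 1000 subjects per group (Protocol 9.1).

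**Assumptions, not in the documents.** γ from 1% to 30%; v_com about 2,900 (roughly 3000 subjects less model terms), with 2,000 as a check; v* = 1/(1/v + 1/v_obs); v_obs = (1 − γ)((v_com + 1)/(v_com + 3))v_com. The SAP states no numerical degrees of freedom or interval width, so there is no figure of its own to reproduce.

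**Step 1: the algebra.** From the printed T and γ,

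1/γ = T/[((D+1)/D)B] = 1 + [D/(D+1)]W/B.

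B is a sample variance with divisor D − 1. Moment (Satterthwaite) matching on T, with W treated as fixed, gives

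v = (D − 1)T²/[((D+1)/D)B]² = (D − 1)/γ² = (D − 1)(1 + [D/(D+1)]W/B)².

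The printed coefficient is 1/101 = 0.0099; the consistent one is 100/101 = 0.990.

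**Step 2: one case by hand, γ = 5%.** Here W/B = 0.95 × 1.01/0.05 = 19.19.

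- Printed: 99 × (1 + 19.19/101)² = 99 × 1.19² = 140.
- Consistent: 99 × (1 + 0.990 × 19.19)² = 99 × 20² = 39,600.
- v_obs = 0.95 × (2901/2903) × 2900 = 2,753.
- v* = 133 (printed) against 2,574 (consistent).
- Critical values are 1.9779 and 1.9609, so the interval is 1.9779/1.9609 − 1 = 0.87% too wide.

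**Step 3: across the assumed range (v_com = 2,900).**

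| γ | v printed | v consistent | v* printed | v* consistent | t printed | t consistent | CI wider by |
|---|---|---|---|---|---|---|---|
| 1% | 392 | 990,000 | 345 | 2,861 | 1.967 | 1.961 | 0.31% |
| 2% | 220 | 247,500 | 204 | 2,808 | 1.972 | 1.961 | 0.55% |
| 5% | 140 | 39,600 | 133 | 2,574 | 1.978 | 1.961 | 0.87% |
| 10% | 118 | 9,900 | 113 | 2,064 | 1.981 | 1.961 | 1.03% |
| 20% | 107 | 2,475 | 102 | 1,197 | 1.983 | 1.962 | 1.09% |
| 30% | 104 | 1,100 | 99 | 713 | 1.984 | 1.963 | 1.07% |

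The last column is the same with v_com = 2,000. Below 1% the effect fades: 0.14% at γ = 0.5% and 0.01% at γ = 0.1%.

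**Step 4: consequences.** The effective two-sided level is 4.93% at γ = 1% and about 4.75% at 20% to 30%. A statistic of 1.97 has p = 0.049 with the consistent v. With the printed v it has p = 0.0496 at γ = 1%, 0.0502 at 2% and 0.0516 at 30%.

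For the weakest planned contrast (Patient's Global Assessment, 2.5 mg; difference 0.11, SD 0.92, from Protocol 9.1), the noncentrality is 0.11/(0.92 × √(2/1000)) = 2.67. Power for that contrast alone goes from 76.2% to 76.0% at γ = 1%, and from 76.1% to 75.4% at 30%.

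**The case against.** **The link from γ to v is not printed.** The appendix gives T and γ but never says v = (D − 1)/γ². That is true. But the relation follows from the SAP's own T and from the D − 1 divisor of B by ordinary moment matching, so no outside source is needed.

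**The text may be damaged.** In the same block v* appears without an inverse and the v_obs denominator reads as a subscript. Both may be losses from reading the PDF, and neither is counted as an error here. The fraction in v, by contrast, is complete and well formed, and the neighbouring (D+1)/D and 1 + 1/D came through cleanly. A misread symbol cannot be excluded outright, so a look at the original page is sensible.

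**Nobody would use it as written.** Taken literally, v* = 1/v + 1/v_obs is about 0.003 to 0.010 degrees of freedom over the assumed range, which is unusable. An analyst who repairs v* might repair v too, and standard software may avoid the problem. That is plausible, but the analysis would then depart from its own written description, which Sections 7 and 8.1.1 make the reference.

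**The effect is tiny and conservative.** This stands, and it is why the point is minor.

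**Conclusion.** The concern holds. The printed v is inconsistent with the T and γ in the same appendix: its coefficient on W/B is too small by a factor of 100 at D = 100, and nothing elsewhere in the SAP corrects it. If it is followed, intervals from the multiple-imputation analyses, including all three co-primary endpoints, are about 0.3% to 1.1% too wide.

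That size rests on γ between 1% and 30%, on v_com of about 2,000 to 2,900, and on reading v* as the inverse of the printed sum. The algebraic inconsistency rests on none of these. The direction is conservative, and only a test statistic falling between roughly 1.96 and 1.98 could change its conclusion. This is a minor error in a prespecified rule.

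**What to change.** In Appendix 3.2, replace 1/(D+1) with D/(D+1), so that v = (D − 1)(1 + [D/(D+1)]W/B)². While the page is open, look at the original file to confirm how the fraction in v is printed, that v* carries the exponent −1, and that the v_obs denominator is v_com + 3. Correct the last two only if they are wrong there.

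The cost is one factor in one formula plus a check of the neighbouring symbols. Design, data collection and the imputation model are untouched, and the primary inference becomes reproducible from the SAP text.
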